4.0 STUDY DESIGN

4.1. Inclusion Criteria

4.1.1 All Patients

- Adults aged 18 years or greater.
- All patients or legal guardians must be willing and able to sign a written informed consent and HIPAA authorization in accordance with local and institutional guidelines.
- Presence of at least 1 measurable lesion \geq 1 cm in size.
- Patients must be willing to have their clinical records reviewed for at least 24 months after enrollment.
- Patients must be willing to lie flat on their back in the PET/CT scanner for up to one hour to allow for the imaging data to be obtained.
- Patients must be willing to undergo two separate PET/CT exams on different days within 2 weeks of each other.
- Determination of pregnancy status: Female patients who are not postmenopausal or surgically sterile will undergo a serum pregnancy test prior to baseline and the subsequent set of multi-tracer PET scans. The serum pregnancy test must be performed within 48 hours prior to research PET imaging. A negative test will be necessary for such patients to undergo research PET imaging. This only applies to Arms 1-2, since only males will be included in Arm 3 (only males can get prostate cancer).

4.1.2 Patients in Arms 1-2

- Patients with known or suspected somatostatin receptor-positive neuroendocrine tumor (NET) who could be considered for clinical use of DOTATATE PET/CT imaging under the approved indications for use of this radiopharmaceutical according to published appropriate use criteria [97]. These indications include: initial staging after the histologic diagnosis of NET; evaluation

of an unknown primary; evaluation of a mass suggestive of NET not amenable to endoscopic or percutaneous biopsy; staging of NET before planned surgery; monitoring of NET seen predominantly on SSTR PET; evaluation of patients with biochemical evidence and symptoms of a NET; evaluation of patients with biochemical evidence of a NET without evidence on conventional imaging or a prior histologic diagnosis; restaging at time of clinical or laboratory progression without progression on conventional imaging; and new indeterminate lesion on conventional imaging with unclear progression.

4.1.3 Patients in Arm 3

- Patients with known or suspected prostate cancer who could be considered for clinical use of PSMA PET/CT imaging under the approved indications for use of this radiopharmaceutical, including: patients with suspected metastasis and patients with suspected recurrence based on elevated serum prostate-specific antigen (PSA) level.

4.2. Exclusion Criteria

[figure not shown]
- Patients with known intolerance or hypersensitivity to any somatostatin analogs will be excluded from the study Arms involving DOTATATE (Arms 1-2).
- Patients with known allergic or hypersensitivity reactions to previously administered radiopharmaceuticals
- Patients who require monitored anesthesia for PET/CT scanning.
- Patients who are too claustrophobic to undergo PET/CT scanning.
- Patients who exceed the 450 lb. weight limit of the PET/CT scanner.
- Patients who are pregnant or currently breast feeding.

4.3. Patient Registration

Participants must meet all of the eligibility requirements listed above prior to registration. Following appropriate pre-registration evaluation, informed consent will be obtained by the study coordinator. The study coordinator will also record study data on all patients entered into the study and complete subsequent forms.

4.4. Study Procedures, Schedule of Events, PET Tracer Administration: Route and Dosing

Patients enrolled in this study will receive all standard of care procedures as determined by their oncologist. The PET/CT exams performed at part of this study will be interpreted a nuclear medicine physician (sub-investigator [name]) and reported as a research note in the electronic health record. Identification of suspected lesions will be performed by the same physician and used for analysis as described below in the methods section.

The PET/CT exams may be performed in either order: FDG first or second, according to scheduling considerations and at the Investigator's discretion.

4.4.1. Initial Visit Prior to PET Imaging

Upon enrollment in the study, the patient will be evaluated by one of the HCI oncologists with verification of informed consent. The following additional patient data will be obtained: histological diagnosis (when available following biopsy or surgery), age, gender, and other treatment modalities used. Clinical (non-research related) PET/CT imaging studies as acquired according to standard of care will be retrieved and loaded into the research database.

4.4.2. Research PET/CT Exams

Patients will receive two research PET/CT exams with two PET tracers: FDG + Cu64-DOTATATE (Arm 1), FDG + Ga68-DOTATATE (Arm 2), or FDG + Ga68-PSMA-11 (Arm 3). The cost of these exams will be covered by the study. The order of the scans with each tracer is not important and will be determined according to scheduling considerations. Female patients who are not postmenopausal for a minimum of one year, or surgically sterile, must have a serum pregnancy test performed within 48 hours prior to each research PET/CT exam (Arms 1-2 only; no females will be enrolled in Arm 3).

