2.2.3. FDG, DOTATATE, and Neuroendocrine Tumors

Neuroendocrine tumors, including gastrointestinal NET, pancreatic NET, pulmonary carcinoids, and other rare NET, have an annual incidence of about 5 per 100,000 in the US. Symptoms can be vague, diagnosis is often made at an advanced stage, and selecting the optimal treatment strategy is challenging. Patients with high uptake of DOTATATE (or other SSTR PET tracers) typically have a more indolent tumor and are more amendable to treatment with Lu177 DOTATATE (Lutathera™), while those with high FDG uptake are more aggressive and are best treated by other methods. Combined imaging of FDG and SSTR tracer avidity has previously been proposed for optimal characterization of NETs [34]. Current approaches use biopsies of the initial tumor to assess differentiation status of tumor cells, and then subsequently prescribe either DOTATATE or FDG imaging for well-differentiated and poorly-differentiated tumors, respectively. However, biopsies provide limited sampling, different groups of cells may exhibit different levels of differentiation, and tumors may initially present as well-differentiated but undergo transformation into higher grade over time with the development of treatment resistance [85]. NETs may also exhibit different degrees of differentiation *simultaneously* in the same patient. Combined imaging of FDG+DOTATATE can provide high sensitivity for both well- and poorly-differentiated NETs, improve staging and grading, and provide more accurate prognosis, and predicting effectiveness of targeted radionuclide therapy [26, 32, 86, 87]. Chan *et al.* [35] state “*it is clear that the time has come to think about FDG and SSRI in metastatic NET not as competitors but as complementary imaging modalities*”. Proposed dual-tracer “NETPET scores” [34] and three-scale combined grading system [17] also highlight the need for combined dual-tracer FDG+DOTATATE of NETs.

There are currently 3 DOTA-conjugated peptide PET tracers with FDA approval for localization of somatostatin receptor positive NETs: Cu64-DOTATATE, Ga68-DOTATATE, and Ga68-DOTATOC [16, 20, 26, 27, 38, 48, 49, 88-93]. Each experiences similar uptake and distribution in the body, but have different radioisotopes: Cu64 ($T_{1/2}=12.70$ h, cyclotron-produced, centrally distributed [94, 95]) vs. Ga68 ($T_{1/2}=67.71$ m, generator-produced locally). We include both Cu64 DOTATATE (Arm 1) and Ga68 DOTATATE (Arm 2) in this study.

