2.2.5. Challenges of Dual-Tracer Imaging

Currently, obtaining FDG & DOTATATE or FDG & PSMA PET images in a given patient requires that separate scans be performed on separate days to allow for radioactive decay of the first tracer before imaging the second. This requires the patient to go to the imaging center twice (particularly burdensome for patients who must travel to reach the clinic), repeat pre-scan procedures, and undergo separate PET exams—each with its own CT component and associated radiation exposure. The time, logistical challenges, expense, and undue patient burden associated with bringing a patient back for separate PET scans on separate days has generally blocked patients from receiving both FDG and DOTATATE or PSMA PET/CT scans—especially considering that they also typically undergo other diagnostic procedures in the short time window before starting treatment.

The ability to image both tracers *simultaneously* in a *single* PET/CT exam would greatly improve the patient experience, require only a single trip to the imaging center, simplify scheduling demands, and reduce overhead. It would also reduce technologist workload: the patient would only need to be positioned once; only one CT scan would be needed for PET attenuation correction (thereby reducing radiation exposure to the patient). In addition, the images would be ‘natively’ co-registered since the patient remains ~motionless on the imaging table for all scans (frame-by-frame image co-registration may still be required in the event of patient motion while scanning). Simultaneous dual-tracer imaging would also benefit the imaging clinic by greatly increasing throughput and improving utilization of the PET/CT scanner resource.

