4.4.4. Day of Study: Single-Tracer FDG PET/CT Exam (all Arms)

FDG PET Tracer Administration:

The patient will be taken to the tracer uptake room, seated comfortably, and have the appropriate IV access placed for tracer administration. The PET technologist will administer approximately 15 mCi of FDG intravenously, and the patient will remain resting during the tracer uptake period (90 min. until start of PET scanning). The patient will be encouraged to hydrate and void their bladder. After the uptake period, the patient will be moved to the PET/CT scanner.

Topogram and CT Scan:

Patients will be positioned on the scanner bed, and will be instructed to remain motionless for the duration of the scan. A CT topogram will be obtained, and the PET imaging field-of-view (FOV) selected. The scanner bed position will be recorded. A CT scan for PET attenuation correction and anatomic localization will then be performed.

Multi-Timepoint PET Scan:

The PET scan will then be acquired, acquiring 5 back-to-back “whole-body” (eyes-to-thighs, or similar) scans, providing 5 sequential PET images. Each pass will take approx. 10 min., for a total scan time of approx. 50 min.

Patient Positioning:

The patient position, bed position, and PET scan FOV will be recorded from the first PET/CT exam. These data will be used to re-position the patient, bed, and FOV for the second PET/CT to match those for the first exam, as possible.

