One challenge of evaluating rapid multi-tracer PET techniques is the need to know the ground truth when evaluating results. For example, one possible study design would be to obtain separate, single-tracer scans with each tracer on separate days, and then to obtain simultaneous dual-tracer scans on a 3rd day—all in the same patient. Here the separate-scan images of each tracer could be used as the standard for evaluating images of each tracer recovered from the dual-tracer scans. However, such an approach would pose many problems, in particular: (1) high cost, scheduling challenges, and patient compliance issues for performing 3 different PET/CT exams on 3 different days; (2) increased radiation exposure from 3 PET/CT exams (3 CTs and 4 total PET tracer administrations); (3) test-retest variability for PET is on the order of 10-15% [99-101]—differences that can be larger than the errors in recovered dual-tracer images and thus limit the value of the study; and (4) it would only allow for a single dual-tracer scanning protocol to be studied (rather than allowing for various scanning protocols to be studied and compared).

A better and widely-accepted approach, used by our group and others [2-8, 10-13] is to acquire separate, single-tracer PET scans with each tracer and then retroactively combine the images to “synthesize” dual-tracer images which are ~identical to the images that would have been obtained from actual dual-tracer scanning. When more than one PET tracer is present during a scan, the resulting image represents the sum of all tracer present. As such, the images from separate, single-tracer PET scans can be added together to create “synthesized” multi-tracer PET images. Aside from small differences in scanner deadtime and random coincidence rates (which are well-understood and accurately corrected by the PET scanner), such synthesized dual-tracer images accurately mimic actual multi-tracer PET images, which characteristics that closely match what would have been obtained from actual multi-tracer scanning.

The advantage of this approach is that the actual single-tracer components of the resulting dual-tracer images are known exactly — and they can be used to evaluate the accuracy of individual-tracer images recovered from the multi-tracer images. In effect, the data become their own controls when using this approach.

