11.0 APPENDIX A: Schedules of Events

Assessment / Procedure	Screening	Imaging Session #1	Imaging Session #2
Informed Consent	X		
Inclusion/ Exclusion Criteria	X		
Pregnancy Test		X ¹	
F18-FDG PET/CT Imaging		X ²	
Cu64-DOTATATE PET/CT Imaging			X ³

- 1) Patient must be postmenopausal for a minimum of one year, surgically sterile, or confirmed not to be pregnant by serum pregnancy test performed within 48hrs prior to PET imaging.
- 2) Subjects will be required to fast for at least 4 hours prior to the scan, drinking only sips of water within 4 hours of the scan if needed for administration of medications.
- 3) The Cu64-DOTATATE PET/CT imaging is performed on a separate day, either before or after the day of the FDG PET/CT imaging.

Assessment / Procedure	Screening	Imaging Session #1	Imaging Session #2
Informed Consent	X		
Inclusion/ Exclusion Criteria	X		
Pregnancy Test		X ¹	
F18-FDG PET/CT Imaging		X ²	
Ga68-DOTATATE PET/CT Imaging			X ³

- 1) Patient must be postmenopausal for a minimum of one year, surgically sterile, or confirmed not to be pregnant by serum pregnancy test performed within 48hrs prior to PET imaging.
- 2) Subjects will be required to fast for at least 4 hours prior to the scan, drinking only sips of water within 4 hours of the scan if needed for administration of medications.
- 3) The Ga68-DOTATATE PET/CT imaging is performed on a separate day, either before or after the day of the FDG PET/CT imaging.

Assessment / Procedure	Screening	Imaging Session #1	Imaging Session #2
Informed Consent	X		
Inclusion/ Exclusion Criteria	X		
F18-FDG PET/CT Imaging		X ¹	
Ga68-PSMA-11 PET/CT Imaging			X ²

- 1) Subjects will be required to fast for at least 4 hours prior to the scan, drinking only sips of water within 4 hours of the scan if needed for administration of medications.
- 2) The Ga68-PSMA-11 PET/CT imaging is performed on a separate day, either before or after the day of the FDG PET/CT imaging.

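### Arm 1 lets FDG follow Cu64-DOTATATE the next day, when 27% of the Cu64 has not decayed; FDG first would all but remove the residual, and a 72 h gap would cut it to about 2%.

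*Combined protocol and SAP*

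**What the plan says.** Section 2.2.5 gives the reason for two imaging days. Obtaining both images currently requires that "separate scans be performed on separate days to allow for radioactive decay of the first tracer before imaging the second".

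The study's own rules do not secure that decay:

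- Section 4.1.1: "Patients must be willing to undergo two separate PET/CT exams on different days within 2 weeks of each other".
- Section 4.4: "The PET/CT exams may be performed in either order: FDG first or second, according to scheduling considerations and at the Investigator's discretion".
- Section 4.4.2: "The order of the scans with each tracer is not important and will be determined according to scheduling considerations".
- Appendix A, Arm 1 footnote: "The Cu64-DOTATATE PET/CT imaging is performed on a separate day, either before or after the day of the FDG PET/CT imaging".

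There is an upper limit on the interval but no lower limit in hours. No check or correction for residual activity is described.

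Section 2.2.3 gives half-lives of 12.70 h for Cu64 and 67.71 min for Ga68. Section 6.1 rests the evaluation on the claim that "the actual single-tracer components of the resulting dual-tracer images are known exactly". Section 6.2.3 asks for a regression slope within 5% of 1 and for SUVs within 0.05 of the reference, with no unit given for the 0.05. Section 6.3 sizes the study on a relative difference of 5%.

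**The concern.** Calling the order unimportant is right for Ga68, which is essentially gone by the next day. It is not right for Cu64 when Cu64 is given first and FDG follows within about three days. The FDG exam then records F18 and leftover Cu64 together, yet its image is filed as single-tracer FDG.

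The extra signal is not spread evenly. It is largest where DOTATATE uptake is high and FDG uptake is low, the pattern Section 2.2.2 expects in well-differentiated tumours. In an affected pair the FDG reference is too high in those lesions. A separation algorithm that correctly assigned the residual to Cu64 would be scored as having made an FDG error.

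The residual also decays more slowly than F18, so its share grows across the five passes. Section 6.2 bases the algorithms on differences in decay and kinetics, so this disturbs the time pattern they are meant to use.

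**Working it through.** The plan states no residual fraction or minimum gap, so there is no figure of its own to reproduce on this point.

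**Inputs from the documents.** Cu64 half-life 12.70 h and Ga68 half-life 67.71 min (Section 2.2.3); Cu64-DOTATATE 4 mCi with 75 min uptake (4.4.5); FDG 15 mCi with 90 min uptake and five passes of about 10 min (4.4.4).

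**Assumptions not in the documents.** F18 half-life 110 min; ratio of Cu64 to F18 positron yield 0.1–0.3; lesion retention of DOTATATE 0.5–1.0; illustrative DOTATATE:FDG SUV ratios.

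**Step 1: share of dose left by physical decay, 2^(−t/T½).**

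- Cu64 at 24 h: 2^(−24/12.70) = 27.0%. At 48 h: 7.3%. At 72 h: 2.0%.
- A 16 h overnight gap also counts as different days and leaves 41.8%.
- Ga68 at 24 h: 2^(−1440/67.71) = 4×10⁻⁷, so Arms 2 and 3 are not affected.

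**Step 2: activity at the start of the FDG scan, with FDG injected 24 h after Cu64.**

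- F18: 15 × 2^(−90/110) = 8.51 mCi.
- Cu64: 4 × 2^(−25.5/12.70) = 0.995 mCi.

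**Step 3: residual as a share of FDG lesion signal.** At equal SUV the share is k = (Cu64 mCi × yield ratio × retention) / F18 mCi. At 24 h:

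- low end: 0.995 × 0.1 × 0.5 / 8.51 = 0.00585
- high end: 0.995 × 0.3 × 1.0 / 8.51 = 0.0351

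At other SUV ratios the share is k × ratio. The 5% line is crossed at a ratio of 0.05/k.

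| Gap between injections | Share at equal SUV (k) | Share at ratio 3 | Ratio at which 5% is reached |
|---|---|---|---|
| 24 h | 0.6–3.5% | 1.8–10.5% | 1.4–8.6 |
| 48 h | 0.16–0.95% | 0.5–2.8% | 5.3–32 |
| 72 h | 0.04–0.26% | 0.13–0.77% | 20–118 |

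At 72 h and a ratio of 10 the share is 0.4–2.6%. If the 0.05 in Section 6.2.3 means SUV units, the residual is k × DOTATATE SUV, and the last column gives the DOTATATE SUV that uses up the margin.

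**Step 4: change across passes.** Pass 5 starts at 130 min, when F18 is 15 × 2^(−130/110) = 6.61 mCi and Cu64 is 4 × 2^(−26.17/12.70) = 0.959 mCi. The share relative to pass 1 is (0.959/6.61) / (0.995/8.51) = 1.24, which is 24% higher.

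**Step 5: pooled effect.** Suppose s of the 15 Arm 1 pairs are next-day Cu64-first, with equal numbers of regions per subject. A shift of 0.05 SUV in mean FDG then needs a mean DOTATATE SUV of 0.05 / (k × s/15).

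- s = 1: 21–128.
- s = 3: 7–43.
- Order split evenly and gaps uniform over 1–14 days (illustrative): the mean of k over all pairs is 0.00029–0.00172, so the SUV needed is 29–175.

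**Step 6: reverse order.** With FDG first and Cu64 injected 24 h later, the Cu64 scan at 75 min has F18 equal to 15 × 2^(−1515/110) = 0.00107 mCi and Cu64 equal to 4 × 2^(−1.25/12.70) = 3.74 mCi. Dividing 0.00107/3.74 by the yield ratio gives 0.10–0.29% of Cu64 signal at equal SUV.

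**The case against.** The best reply is that this is narrow and may never occur. It needs Arm 1 (15 of 50 subjects), Cu64 first, and FDG within about three days of a two-week window. Section 4.4 leaves the order to the investigator, and Section 2.2.5, which describes current practice rather than a study rule, shows that the team knows why the gap exists. The size of the image error depends on yield, retention and uptake ratios that the documents do not give, and the 24 h break-even ratio spans a sixfold range. The targets are judged over many regions, not lesion by lesion. The study collects data for algorithm development, and the error makes its targets harder to meet.

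Most of this stands, and it limits the claim. The frequency is unknown, a pooled effect is not shown, and no false finding of equivalence follows. Two parts do not remove the point. Discretion is weak protection when Section 4.4.2 tells the same investigator that order does not matter. And the primary objective in Section 1.1 is data suitable for building these algorithms, so a contaminated reference matters for the pair concerned even if averages barely move.

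The calculation covers the FDG channel only. The effect on the Cu64 channel of moving the residual there is not worked through and could be relatively larger in an affected pair.

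**Conclusion.** The concern holds. The protocol permits next-day FDG after Cu64-DOTATATE, and the missing rule can contaminate an image that the analysis treats as exact. The 27% follows from the protocol's half-life alone; biological clearance would lower it. The image error rests on the stated assumptions. Under them, a next-day residual can exceed 5% of the FDG signal, or 0.05 SUV, in individual DOTATATE-avid, FDG-poor lesions. A pooled effect is unlikely unless several pairs are scheduled this way. The change is recommended because it costs little, not because harm to the pooled result has been demonstrated.

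**What to change.** Amend Sections 4.4 and 4.4.2 and the Arm 1 footnote in Appendix A to require FDG first in Arm 1. Where Cu64-DOTATATE must come first, require at least 72 h from the Cu64 injection to the FDG injection. FDG first all but removes the problem. The 72 h gap reduces it: at a ratio of 3 the residual stays below 1% at the upper end of the assumed range, even at the start of pass 5 (0.77% × 1.24 = 0.95%).

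Record both injection times. For pairs already acquired Cu64-first with a shorter gap, report the Section 6.2.3 targets with and without them. Define that set by time gap alone, not by lesion signal ratio, so that DOTATATE-avid, FDG-poor lesions are not selectively dropped.

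The cost is wording in two sections and one footnote, for one arm. Both options fit the two-week window and add no scan or radiation. Arm 1 loses some scheduling freedom, which may matter because Cu64 is centrally supplied (Section 2.2.3); the 72 h alternative covers cases where FDG first cannot be arranged.

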4.4.3. Restrictions in 24 Hour Period Prior to PET/CT Exams

- **FDG Scans:** Patients will be asked to minimize physical activity 24 hours prior to scans with FDG. They will also be required to fast for 6 hours prior to the FDG injection. Patients can take all required medications with water.
- **DOTATATE and PSMA Scans:** There are no dietary restrictions for patients prior to receiving PET/CT scans with these tracers.

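### The Arm 1 and Arm 2 schedules mark the pregnancy test at the first imaging session only, although Section 4 calls for it before both exams; the FDG fasting rules also differ (minor)

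*Combined protocol and SAP*

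**What the plan says.** **Pregnancy test (Arms 1 and 2).** For women who are neither postmenopausal nor surgically sterile, Section 4.4.2 states that they "must have a serum pregnancy test performed within 48 hours prior to each research PET/CT exam". Section 4.1.1 says that such patients "will undergo a serum pregnancy test prior to baseline and the subsequent set of multi-tracer PET scans", sets the same 48 h window, and adds: "A negative test will be necessary for such patients to undergo research PET imaging". The spacing of the exams is also in Section 4.1.1: "Patients must be willing to undergo two separate PET/CT exams on different days within 2 weeks of each other".

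The Arm 1 and Arm 2 schedules in Appendix A each carry one pregnancy-test mark. It stands under Imaging Session #1, in the same column as the FDG exam, and the Imaging Session #2 cell is empty. Footnote 1 asks that the patient, if not postmenopausal or sterile, be "confirmed not to be pregnant by serum pregnancy test performed within 48hrs prior to PET imaging". Footnote 3 lets the DOTATATE exam fall "either before or after the day of the FDG PET/CT imaging".

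**FDG preparation (all arms).** Section 4.4.3 says of patients having FDG: "They will also be required to fast for 6 hours prior to the FDG injection". The footnote in all three schedules says: "Subjects will be required to fast for at least 4 hours prior to the scan". It limits water in those 4 h to sips for taking medication. Section 4.4.4 sets a 90 min uptake period from injection to the start of PET and encourages hydration.

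**The concern.** Coordinators commonly book visits and laboratory work from the schedule of events. Here the schedule is less demanding than the text it summarises, on a check meant to keep pregnant patients from being irradiated. Anyone following the table would order one test, and the second exam could go ahead on a result older than the 48 h that Section 4.4.2 allows.

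The column layout adds a second ambiguity. The mark shares its column with FDG, yet either tracer may come first. If the columns are read as tracers rather than visits, the table shows no test before a DOTATATE exam done first.

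The protocol's own dosimetry shows what the second exam involves. Tables 1 and 2 give single-scan uterine doses of 9.99 mGy (FDG), 2.81 mGy (Cu64-DOTATATE), 2.78 mGy (Ga68-DOTATATE) and 15.43 mGy (one CT). The second exam therefore adds about 2.78 + 15.43 = 18.21 mGy or 2.81 + 15.43 = 18.24 mGy if it is DOTATATE, and 9.99 + 15.43 = 25.42 mGy if it is FDG.

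The fasting mismatch matters less. Preparation could differ between patients, which bears on FDG SUVs and on the exploratory relative-uptake comparison in Section 1.2. It does not bear on the recovered-versus-true targets in Section 6.2.3, because those compare images from the same acquisitions.

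**Working it through.** The plan gives no figure of its own to reproduce here. The check sets the passages side by side and works out what one test can cover.

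**How many tests does each place call for?**

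| Place | Occasions |
|---|---|
| 4.4.2 | One before each of the two exams |
| 4.1.1 | Most naturally two (baseline and subsequent scans); wording looser |
| Appendix A, Arms 1 and 2, table | One mark, Session #1 |
| Appendix A, footnote 1 | 48 h before PET imaging; no statement about each exam |

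**Can one test serve both exams?** Inputs: a 48 h window (4.1.1, 4.4.2) and a gap of d = 1 to 14 days (4.1.1). Assume that both sessions start at the same clock time. A test taken t hours before Session #1 (0 ≤ t ≤ 48) is t + 24d hours old at Session #2. It covers both only if t + 24d ≤ 48.

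| Gap d | Age of the test at Session #2 | Covers both exams? |
|---|---|---|
| 1 day | 24 to 72 h | Only if t ≤ 24 h |
| 2 days | 48 to 96 h | Only if t = 0 |
| 3 days | 72 to 120 h | Never |
| 14 days | 336 to 384 h | Never |

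Every gap from 3 to 14 days fails, which is 12 of the 14 whole-day gaps. At no gap is coverage guaranteed. The result for 3 days or more does not depend on the clock-time assumption: two whole days lie between the sessions, so more than 48 h always pass.

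**Who is affected?** Arms 1 and 2 have 15 + 15 = 30 subjects. The plan does not say how many will be women to whom the test applies.

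**Fasting on one reference point.** Inputs: 6 h before injection (4.4.3), at least 4 h before the scan (Appendix A), 90 min = 1.5 h uptake (4.4.4).

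- If the scan means the start of PET, the footnote minimum is 4 − 1.5 = 2.5 h before injection. The difference is 6 − 2.5 = 3.5 h.
- If the scan means injection, the difference is 6 − 4 = 2 h.

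Under the first reading, the limit to sips of water also covers the uptake period in which Section 4.4.4 encourages hydration. All 15 + 15 + 20 = 50 subjects have an FDG exam.

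**The case against.** The strongest reply is that the safeguard is already in the protocol. Section 4.4.2 is explicit, Section 4.1.1 makes a negative test a condition of imaging, and Section 4.2 excludes pregnant patients. On this view Appendix A is an incomplete summary. That is a fair account of the mitigation, and the claim is only that the second test could be missed, not that it is waived. The mitigation is partial, though. The negative-test rule is worded in the singular, so the Session #1 result could be taken to satisfy it. Appendix A marks the eligibility check at screening only. Oversight under Section 7.3 is a monthly review by the principal investigator, so an omission might be found only after the exposure.

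The reading of the table can also be questioned. The position of the mark comes from a table extracted by program, and a cell merged across both sessions cannot be fully excluded. This caveat stands. In both schedules, however, the mark lines up with the FDG entry and apart from the DOTATATE entry. Footnote 1 nearly repeats a sentence in Section 4.1.1 and does not by itself contradict Section 4.4.2, but it does not supply the repeat test either.

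Three smaller points are right. Section 4.1.1 speaks of baseline and multi-tracer scans, which do not match a design of two single-tracer exams, so Section 4.4.2 carries the requirement. The figure of 12 of 14 counts permitted gaps, not how often they will occur. Reading the columns as visits is more natural than reading them as tracers.

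On fasting, both rules can be met together because the 4 h is a minimum. That makes it a wording inconsistency and not a direct conflict, and the clash over water arises only if the scan means the start of PET.

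**Conclusion.** The inconsistency on the pregnancy test is real and must be fixed. As printed, the Arm 1 and Arm 2 schedules do not carry the second test that Section 4.4.2 requires, and one test cannot satisfy that section at any gap of 3 days or more. It concerns an unknown number of the 30 subjects in Arms 1 and 2. The grade rests on the nature of the check, which precedes irradiation, and not on a count of patients. The conclusion assumes that the extracted table shows the mark where it is printed.

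The fasting mismatch is also real but minor. The two minimums differ by 2 to 3.5 h, depending on what the scan means. All 50 subjects are covered by it, both rules can be met at once, and the documents give no figure for any effect on SUV.

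**What to change.** 1. Reconcile Sections 4.1.1 and 4.4.2 with the Arm 1 and Arm 2 schedules and their footnote 1 on whether the pregnancy test applies before each imaging session. The table, the footnote and the text should then give the same answer. Bring the terms in Section 4.1.1 into line with a design of two single-tracer exams.
2. State whether the Imaging Session columns mean visit order or tracer, given that either exam may come first.
3. As a separate, lower-priority correction, reconcile Sections 4.4.3 and 4.4.4 with the schedule footnotes on the fasting interval, its reference point (injection or start of PET) and water intake.
4. State each rule once and refer to it elsewhere.

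Which statements stand is for the investigator to decide. The cost is a text amendment of Appendix A or Section 4, submitted for IRB approval as Section 7.4 requires. Design, sample size and analysis do not change.
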